1. INTRODUCTION

This Statistical Analysis Plan (SAP) describes the planned statistical analyses to be performed for data from Protocol TIL2018-1, “An Open Label, Real World Study Evaluating the Long-Term Quality of Life of Tildrakizumab in Adult Patients with Moderate to Severe Plaque Psoriasis”.

This SAP was created using Clinical Protocol TIL2018-1 Version 1.3 dated 02Jan2020, and the electronic Case Report Forms (eCRFs) Version 2.0 dated 02Jul2020.

2. PURPOSE OF THE ANALYSES

The purpose of this SAP is to outline the planned analyses to be completed to support the Clinical Study Report (CSR) for Protocol TIL2018-1. Any post-hoc or unplanned analyses not identified in this SAP will be clearly identified in the CSR.

3. STUDY OBJECTIVES AND ENDPOINTS

3.1 Objectives

The primary objective is to demonstrate improvement from baseline in patient quality of life (QoL) after 28 and 52 weeks of treatment with tildrakizumab, under real world conditions, as measured by Psychological General Well-Being scale (PGWB).

Secondary objectives include assessment of patient quality of life as measured by the Dermatology Life Quality Index (DLQI), work productivity and activity impairment, psoriasis symptom control, patient satisfaction, long-term efficacy, and safety.

3.2 Efficacy Endpoints

3.2.1 Primary

Improvement in quality of life measured by change from baseline in total PGWB score at Week 28 and Week 52

3.2.2 Secondary

1. Improvement in quality of life measured by change from baseline in total PGWB score as well as PGWB scores for subscales in anxiety, depression, positive-well being, self-control, general health and vitality over time (weeks 4, 8, 12, 16, 40, 64)
2. Improvement in quality of life measured by change from baseline in DLQI over time (weeks 4, 8, 12, 16, 28, 40, 52, 64)
3. Proportion of subjects with DLQI score of 0 or 1 at weeks 4, 8, 12, 16, 28, 40, 52, and 64
4. Proportion of subjects with DLQI score <5 at weeks 4, 8, 12, 16, 28, 40, 52, and 64
5. Proportion of subjects with a reduction of ≥ 5 points in DLQI from baseline at weeks 4, 8, 12, 16, 28, 40, 52, and 64

[figure not shown]
6. Efficacy of drug as measured by change in percent affected body surface area (BSA), change in Static Physician's Global Assessment (sPGA), and/or BSAXPGA over time (weeks 4, 8, 12, 16, 28, 40, 52, 64)
7. Efficacy of drug as measured by Psoriasis Area Severity Index (PASI) (% of PASI improvement from baseline, absolute PASI) over time (weeks 4, 16, 28, 52)
8. Improvement from baseline in itch, pain, and scaling using numerical rating scales over time (weeks 4, 8, 12, 16, 28, 40, 52, 64)
9. Proportion of patients with itch score of 0, pain score of 0, and scaling score of 0, respectively, at weeks 4, 8, 12, 16, 28, 40, 52, and 64
10. Improvement from baseline in work productivity measured by change in Work Productivity and Activity Impairment scale (WPAI-PSO) over time (weeks 16, 28, 40, 52, 64)
11. Assessment of patient satisfaction with treatment measured with Treatment Satisfaction Questionnaire for Medication (TSQM) over time (weeks 4, 8, 12, 16, 28, 40, 52, 64)
12. Tildrakizumab overall satisfaction over time (weeks 4, 8, 12, 16, 28, 40, 52, 64)
13. Patient happiness with psoriasis control over time (weeks 4, 8, 12, 16, 28, 40, 52, 64)

3.3 Safety Endpoints

Incidence (severity and causality) of any local and systemic adverse events (AEs).

4. STUDY DESIGN

This is a Phase 4 multicenter, uncontrolled open-label study design. There will be a total of 10 study visits at Screening, Baseline, Week 4, Week 8, Week 12, Week 16, Week 28, Week 40, Week 52 and Week 64, with subjects receiving tildrakizumab injections at Week 0, Week 4, Week 16, Week 28, Week 40, and Week 52. The total study duration will be approximately 64 weeks, excluding a screening period. Approximately 60 subjects will be enrolled into the study at two sites. For an individual subject, the study duration should be approximately 64 weeks. The duration of the study as a whole will vary based upon the rate of recruitment and completion of subjects.

5. DEFINITIONS

- The **Study Day** is the day of the study relative to the [REDACTED] dose [REDACTED] of the study product.
- The **baseline assessment** is defined as the [REDACTED] measurement collected at [REDACTED] to the [REDACTED] application of the study product.
- **Change from Baseline** will be calculated as: [REDACTED]

Correspondingly, **percentage change** will be calculated as: [REDACTED]

6. CLINICAL EVALUATIONS

6.1 Body Surface Area

The percent BSA affected with psoriasis will be estimated at each study visit. [REDACTED]

6.2 Static Physician's Global Assessment

The sPGA is used to determine the overall severity of psoriasis lesions at a given time point. The investigator will obtain the final sPGA score according to following classification:

[REDACTED]	[REDACTED]

6.3 Psoriasis Area Severity Index

The PASI is a quantitative rating scale for measuring the severity of psoriatic lesions based on area coverage and plaque appearance. PASI analyzes the four regions of the body (head, trunk, upper and lower limbs). [REDACTED]

[REDACTED]. A higher score indicates more severe disease.

6.4 Itch Numerical Rating Scale

The Itch-Numerical Rating Scale (I-NRS) is a simple, [REDACTED] self-administered numeric rating scale. At [REDACTED] visit, subjects indicate itch severity by circling the integer that best describes the worst level of itching due to psoriasis in the past [REDACTED] on an [REDACTED] scale [REDACTED].

6.5 Pain Numerical Rating Scale

The Pain-NRS (P-NRS) is a simple, [REDACTED] self-administered numeric rating scale that is administered at each visit. Subjects indicate skin pain severity by circling the integer that best describes the worst level of skin pain due to psoriasis in the past [REDACTED] on an [REDACTED]

6.6 Scaling Numerical Rating Scale

The Scaling-NRS (S-NRS) is a simple, [REDACTED] self-administered numeric rating scale that is administered at each visit. Subjects indicate scaling severity by circling the integer that best describes the worst level of scaling due to psoriasis in the [REDACTED]

6.7 Psychological General Well-Being Index

The PGWB is a self-administered validated psychometric instrument that measures a person's emotional well-being. It is specifically designed to be suitable for assessing psychological well-being in the general medical population as opposed to a psychiatric population. The 22 questions of the PGWB can be further divided into 6 domains: anxiety

[REDACTED], depressed mood [REDACTED], positive well-being [REDACTED],
[REDACTED], self-control [REDACTED], and vitality [REDACTED]

[REDACTED]. The global score is calculated by summing up all of the single items and thus has a hypothetical range from 0-110 score points, with higher scores indicating better psychological wellbeing.

A series of 12 horizontal black bars of varying lengths, decreasing from left to right. The bars are positioned at different vertical intervals, creating a stepped effect. The first bar is the longest and is located at the top. The last bar is the shortest and is located at the bottom. The bars are set against a white background.

6.8 Dermatology Life Quality Index

The DLQI is a self-administered and user-friendly validated questionnaire used to measure the health-related quality of life of adult patients suffering from a skin disease. It consists of [REDACTED] questions concerning patients' perception of the impact of skin diseases on different aspects of their health related quality of life over the last week. The items of the DLQI encompass aspects such as symptoms and feelings, daily activities, leisure, work or school, personal relationships and the side effects of treatment. Scores of individual items [REDACTED] are added to yield a total score [REDACTED]

[REDACTED] Higher scores mean greater impairment of patient's QoL.

6.9 Work Productivity and Activity Impairment Scale

The WPAI is a validated, subject-reported quantitative assessment of the amount of absenteeism, presenteeism and daily activity impairment attributable to general health or a specific health problem. WPAI surveys were analyzed based on published algorithms to determine the following: current employment status, absenteeism [REDACTED], presenteeism [REDACTED] total activity impairment [REDACTED], and total work productivity impairment [REDACTED]

[REDACTED] higher scores representing greater impairment (worse outcomes).

6.10 Treatment Satisfaction Questionnaire for Medication

The TSQM is a general measure of treatment satisfaction with medication, suitable for use across a wide variety of medication types and illness conditions. The [REDACTED] TSQM Version 1.4 is a reliable and valid instrument to assess patients' satisfaction with medication, providing scores on four scales – side effects, effectiveness, convenience and global satisfaction.

TSQM consists of fourteen questions. It will be computed and summarized by adding the items in each of the four domain below. This provided a transformed score between [REDACTED] that should be

multiplied by $\boxed{}$. $\boxed{}$ higher scores representing higher satisfaction on that domain.

A series of nine horizontal black bars of varying lengths, decreasing from left to right. The bars are positioned at different vertical intervals, creating a stepped effect. The first bar is the longest and is located at the top. The second bar is shorter and is located below the first. The third bar is the shortest and is located below the second. The fourth bar is longer than the third and is located below the second. The fifth bar is longer than the fourth and is located below the third. The sixth bar is longer than the fifth and is located below the fourth. The seventh bar is longer than the sixth and is located below the fifth. The eighth bar is longer than the seventh and is located below the sixth. The ninth bar is the longest and is located at the bottom.

6.11 Tildrakizumab Overall Satisfaction

The Tildrakizumab Overall Satisfaction Scale is a simple, [REDACTED] self-administered numeric rating scale that is administered at each visit starting at Visit 3 (Week 4). Subjects indicate their overall satisfaction with the use of tildrakizumab as well as on specific areas by circling the integer that best describes their experience on an [REDACTED] scale [REDACTED]

1. **What is the primary purpose of the proposed legislation?**

6.12 Patient Happiness with Psoriasis Control

The Patient Happiness with Psoriasis Control assessment is a simple, [REDACTED] self- administered numeric rating scale that is administered at each visit.

Subjects indicate their overall happiness with psoriasis control by circling the integer that best describes their experience on an [REDACTED] scale [REDACTED]
[REDACTED]

6.13 Full-Body Photography (excluding face)

Full-body photographs will be taken on consenting subjects. Clinical photographs should be standardized using a solid color background and consistent subject positioning and lighting. Approximately [REDACTED] views should be taken; full front, full back and four half-body views, ensuring that all non-head areas affected by psoriasis are captured. Subjects who refuse to undergo full-body photography may still be enrolled in the study. Photos are only for visual documentation of psoriasis and will not be analyzed.

7. SAFETY EVALUATIONS

7.1 Adverse Events

An AE is any untoward medical occurrence associated with the use of a drug in humans, whether or not considered drug related. An AE (also referred to as an adverse experience) can be any unfavorable and unintended sign (e.g., an abnormal laboratory finding), symptom, or disease temporally associated with the use of a drug, without any judgment about causality. An AE can arise from any use of the drug (e.g., off-label use, use in combination with any drug) and from any route of administration, formulation, or dose, including an overdose. A treatment emergent AE (TEAE) is defined as an AE that started on or after the date of the first dose of test article.

The severity of an AE will be recorded as mild, moderate, or severe. The relationship between an AE and the test article will be classified as definitely related, probably related, possibly related, unlikely related, or not related.

7.2 Blood Chemistry, Hematology, and Virology/ Human Immunodeficiency Virus

Blood samples for laboratory tests are to be taken prior to first administration of test article and should be performed according to standard laboratory procedures. Follow-up labs for chemistry, blood count and virology beyond screening can be done at the clinical judgment of the investigator.

[REDACTED]	[REDACTED]	[REDACTED]

7.3 QuantiFERON-Tuberculosis Gold test

QuantiFERON-Tuberculosis (TB) Gold test is not required at screening for subjects with a history of latent TB and ongoing treatment for latent TB or documentation of having completed appropriate treatment. Subject is to undergo chest x-ray during Screening period if result of QuantiFERON-TB Gold test is positive, or if they have history of latent TB, signs or symptoms suggestive of active TB or had recent close contact with a person with active TB.

7.4 Pregnancy Tests

A serum pregnancy test must be performed on all female subjects of child-bearing potential at [REDACTED] A urine pregnancy test (UPT) will be performed in women of childbearing potential at all visits where study article is administered.

7.5 Physical Exam

A full physical exam including vital signs, height and weight will be performed at [REDACTED]. The limited physical exam with vital signs and weight will be performed at [REDACTED].

8. STATISTICAL METHODS

8.1 General Considerations

All statistical processing will be performed using SAS® Version 9.4 or higher, unless otherwise stated. For continuous variables, descriptive statistics will include the number of subjects with non-missing data (n), mean, standard deviation (SD), median, minimum, and maximum values. For categorical variables, the number and percentage of subjects within each category will be

presented. Subject data listings will be sorted by treatment group, study site and subject number and visit, as applicable.

8.2 Analysis Populations

All subjects will be classified into the Intent-to-Treat (ITT), Per-Protocol (PP), and Safety populations according to the following definitions. Membership in the analysis populations will be determined prior to database lock.

8.2.1 Safety Population

The Safety population will include all subjects who are enrolled

8.2.2 Intent-to-Treat Population

The ITT population will include all subjects who are enrolled

8.2.3 Per-Protocol Population

The Per Protocol Population will include a subset of the ITT population who completed the study and meet the following criteria:

1. Meets all inclusion/exclusion criteria

8.3 Final Analyses and Reporting

Final database lock will occur after all subjects have completed the study assessment period (or discontinued early) and all subject data has been monitored. Analysis may not occur until after this SAP is approved, analysis populations have been identified and database lock.

[figure not shown]
[figure not shown]
8.4 Sample Size

No formal sample size calculations were performed. The sample size of 60 subjects was selected to provide adequate estimates of probable events in the population.

[figure not shown]
8.5 Analysis Visit Windows

Efficacy data will be assigned to analysis visits based on its nominal scheduled visit. Early termination visit will be assigned to analysis visits as defined in the visit window tables below.

Final visit is the subject's last visit. If the subject completed the study, Week 64/Visit 10 will be the last visit; if a subject discontinued, the efficacy data for the last visit will be assigned to the analysis visit defined by the analysis visit window.

¹PASI

8.6 Subject Disposition

The number and percentage of subjects who were enrolled in the study, in each analysis population, who completed the study, who withdrew from the study and their reasons for discontinuation will be summarized.

Protocol deviations will be summarized by total deviations and by deviations type for Safety population with available data, using descriptive statistics.

8.7 Screening and Baseline Assessments

8.7.1 Demographics and Baseline Characteristics

Demographic and baseline characteristics including age, sex, ethnicity and race will be summarized by treatment group for the ITT, PP and Safety populations using descriptive statistics. Demographic data for screen failures will be summarized separately.

8.7.2 Medical History

Medical histories will be provided in a subject listing for the Safety population. Findings noted during the Screening and Baseline physical examinations will be recorded in the medical history.

8.7.3 Psoriasis Treatment History

Psoriasis treatment history will be summarized by number and percentage of subjects for each type of prior treatment and also the number and percentage of subjects with each clinical response for each treatment. A subject listing for individual psoriasis treatment history will be provided.

8.7.4 Physical Examinations

Physical examination results will be included in medical history.

8.7.5 Vital Signs, Height, Weight and Body Mass Index

Descriptive statistics of the observed and change from Baseline values of each vital sign parameter (temperature, systolic and diastolic blood pressure, heart rate, and respiration rate) and weight will be provided for each scheduled visit. Descriptive statistics of height and body mass index will be provided at Screening/Baseline.

8.7.6 Baseline Clinical Evaluations

The Screening and Baseline severity scores for sPGA will be tabulated for the ITT population. Descriptive statistics will be provided for the Screening and Baseline data of BSA, PASI, WPAI-PSO, PGWB, DLQI, I-NRS, P-NRS, S-NRS and Patient Happiness with Psoriasis control.

8.9 Efficacy Evaluation

8.9.1 Analysis of Efficacy

The efficacy analyses will be conducted on the ITT population and repeated on the PP population for selected endpoints. The Safety population will be used for the analyses of safety endpoints.

Change from Baseline for the efficacy variables will be analyzed using the t-test. The 95% 2-sided confidence intervals will be calculated.

For dichotomous response variables, the binomial exact 95% confidence interval will be presented.

For all efficacy by visit analysis, a final visit will be included. The final visit is either Week 64/Visit 10 if a subject completed the study, or the last visit before discontinuation.

BSA

The BSA will be analyzed for the following endpoint:

- Change from Baseline to Weeks 4, 8, 12, 16, 28, 40, 52 and 64, with percent Change from Baseline summarized

sPGA

The sPGA will be analyzed for the following endpoint:

- Change from Baseline to Week 4, 8, 12, 16, 28, 40, 52 and 64
- The proportion of subjects with a ≥ 1 -grade decrease from Baseline to each study visit
- The proportion of subjects with a ≥ 2 -grade decrease from Baseline to each study visit
- The proportion of subjects categorized as 'clear' (0) or 'almost clear' (1) on the sPGA and a ≥ 2 -grade decrease from Baseline to each study visit

BSA x sPGA

The product of BSA x sPGA will be analyzed for the following endpoint:

- Change from Baseline to Weeks 4, 8, 12, 16, 28, 40, 52 and 64, with percent Change from Baseline summarized

PASI

The PASI total score will be analyzed for the following endpoint:

- Change from Baseline to Weeks 4, 16, 28 and 52, with percent Change from Baseline summarized

- [REDACTED]
- [REDACTED]

I-NRS

- Change from Baseline to Weeks 4, 8, 12, 16, 28, 40, 52 and 64, with percent Change from Baseline summarized
- Proportion of patients with I-NRS of 0 at Weeks 4, 8, 12, 16, 28, 40, 52 and 64

P-NRS

- Change from Baseline to Weeks 4, 8, 12, 16, 28, 40, 52 and 64, with percent Change from Baseline summarized
- Proportion of patients with P-NRS of 0 at Weeks 4, 8, 12, 16, 28, 40, 52 and 64

S-NRS

- Change from Baseline to Weeks 4, 8, 12, 16, 28, 40, 52 and 64, with percent Change from Baseline summarized
- Proportion of patients with S-NRS of 0 at Weeks 4, 8, 12, 16, 28, 40, 52 and 64

PGWB

The PGWB score will be analyzed for the following endpoint:

- Change from Baseline to Weeks 4, 8, 12, 16, 28, 40, 52 and 64 in global score, with percent Change from Baseline summarized
- Change from baseline to Weeks 4, 8, 12, 16, 28, 40, 52 and 64 in each of the six sub domain, with percent Change from Baseline summarized

DLQI

DLQI will be analyzed for the following endpoint:

- Change from Baseline to Week 4, 8, 12, 16, 28, 40, 52 and 64 in DLQI total score, with percent Change from Baseline summarized
- The proportion of subjects with DLQI total score of 0 or 1 at Weeks 4, 8, 12, 16, 28, 40, 52 and 64
- The proportion of subjects with DLQI total score ≤ 5 at Weeks 4, 8, 12, 16, 28, 40, 52 and 64
- The proportion of subjects with a reduction of ≥ 5 points in DLQI total score from Baseline at Weeks 4, 8, 12, 16, 28, 40, 52 and 64. Subjects must have Baseline DLQI score of ≥ 5 to be included in this analysis.

WPAI-PSO

Each of the four WPAI-PSO domain scores will be analyzed for the following endpoint:

- Change from Baseline to Weeks 16, 28, 40, 52 and 64. [REDACTED]

TSQM

Each of the four TSQM domain scores at Weeks 4, 8, 12, 16, 28, 40, 52 and 64 [REDACTED]

[REDACTED]

Tildrakizumab Overall Satisfaction

Tildrakizumab Overall Satisfaction score in each of the four specific areas will be summarized for Weeks 4, 8, 12, 16, 28, 40, 52 and 64.

Patient Happiness with Psoriasis Control

Patient Happiness with Psoriasis Control will be analyzed for the following endpoint:

- Change from Baseline to Weeks 4, 8, 12, 16, 28, 40, 52 and 64, with percent Change from Baseline summarized

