10.2. Subject Discontinuation

A subject may be withdrawn from the study prior to completion for any of the following reasons:

- Whenever the subject decides it is in the subject's best interest to withdraw. NOTE: if the subject decides it is in the subject's best interest to withdraw due to an AE then it should be classified as withdrawal due to an AE.
- Whenever the investigator decides it is in the subject's best interest to be withdrawn

- AEs
- Worsening of condition or treatment failure (in the opinion of the investigator)
- Intercurrent illness which may, in the investigator's opinion, significantly affect assessment of clinical status
- Noncompliance
- Lost to follow-up
- Sponsor administrative reasons

If a subject withdraws prematurely during the treatment period, complete the CRF for the appropriate visit, then complete the End of Study CRFs.

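### The primary PGWB change is analysed by a separate t-test at each visit, ignoring earlier scores; a repeated-measures estimate would protect it against response-related drop-out at little cost

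*SAP*

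**What the plan says.** The primary endpoint in SAP 3.2.1 is "Improvement in quality of life measured by change from baseline in total PGWB score at Week 28 and Week 52". The study has one arm and no control; SAP 4 states: "Approximately 60 subjects will be enrolled into the study at two sites".

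SAP 8.9.1 gives one method for all continuous efficacy variables: "Change from Baseline for the efficacy variables will be analyzed using the t-test". It then adds "The 95% 2-sided confidence intervals will be calculated". For PGWB the listed analysis is "Change from Baseline to Weeks 4, 8, 12, 16, 28, 40, 52 and 64 in global score, with percent Change from Baseline summarized". No longitudinal model appears in the legible text.

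Four other provisions bear on missing scores:

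- Protocol 10.2 lists, among the reasons for withdrawal, "Worsening of condition or treatment failure (in the opinion of the investigator".
- SAP 8.5 assigns data from an early-termination visit to an analysis visit by window; the window table is not shown.
- SAP 8.9.1 adds a final-visit row to every by-visit efficacy analysis: "The final visit is either Week 64/Visit 10 if a subject completed the study, or the last visit before discontinuation".
- SAP 8.10.1, on drop-outs and missing data, is in the table of contents, but its text is blacked out.

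**The concern.** A one-sample t-test at Week 52 uses whatever Week 52 values are in the data set. It does not use the scores the same subjects gave at Weeks 4 to 40. If subjects who leave tend to be those whose scores had improved least, and their gaps are left empty, the subjects remaining at Week 52 are a favourable selection.

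Such loss is foreseeable. Besides the withdrawal reason quoted above, Protocol 6.1 prohibits new psoriasis treatments, which gives a poor responder a reason to leave. Protocol 4.3 only encourages attendance after treatment stops, and gives safety as the purpose.

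There is no control arm against which such a shift could cancel. Any bias therefore passes straight into the headline estimate, and the interval around it covers the true mean less often than 95%.

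**Working it through.** **Nothing to reproduce.** The documents give no PGWB standard deviation, expected effect, drop-out rate or power figure. The size of the effect has to be explored under stated assumptions.

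**Inputs from the documents.** N = 60; PGWB at Weeks 4, 8, 12, 16, 28, 40 and 52 (Week 64 is not needed for the primary endpoint); single arm.

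**Assumed inputs.** Changes are normal with SD 1 and equal correlation of 0.5 or 0.7 between visits. The true mean is flat, so the average estimate is the bias. Drop-out is monotone, with logit P(drop at visit k) = a - b × (last observed change). The slope b is 0.5, 1 or 2 per SD, and a is set so that 5, 10, 20 or 30% are lost by Week 52. This is missing at random (MAR). There were 1,500 runs per setting, so the simulation error of a mean is about (1/√60)/√1500 = 0.003 SD.

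**Step 1: no drop-out.** The t-test mean and the unstructured repeated-measures maximum-likelihood mean are identical. If loss is unrelated to response, both are unbiased.

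**Step 2: MAR drop-out.** The table gives bias in SDs of change (positive = too favourable) over the correlations and slopes above.

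| Lost by Week 52 | Observed cases, Week 28 | Observed cases, Week 52 | LOCF, Week 52 | Repeated-measures likelihood |
|---|---|---|---|---|
| 5% | 0.01 to 0.04 | 0.01 to 0.06 | 0.00 to -0.04 | within 0.01 |
| 10% | 0.02 to 0.08 | 0.03 to 0.11 | -0.02 to -0.08 | within 0.01 |
| 20% | 0.04 to 0.16 | 0.06 to 0.21 | -0.03 to -0.16 | within 0.01 |
| 30% | 0.05 to 0.23 | 0.09 to 0.31 | -0.04 to -0.23 | within 0.01 |

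**Step 3: allow for SAP 8.5.** Suppose each drop-out supplies an early-termination value that counts at the first missed visit. At 20% loss, the Week 52 bias falls from 0.12 to 0.10 SD (correlation 0.6, slope 1.0), and from 0.20 to 0.17 SD (correlation 0.75, slope 1.5). The mapping fills one visit only, so earlier drop-outs are still missing at Week 52. Over 10-20% loss, slopes 1.0 to 1.5 and correlations 0.5 to 0.7, the mapped observed-case bias at Week 52 is about 0.04 to 0.16 SD, with coverage of about 79-94%. Flatter or steeper slopes widen the range both ways, as in the table.

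**Step 4: check coverage by hand.** Coverage ≈ Φ(1.96 - bias/SE) - Φ(-1.96 - bias/SE).

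- 10% lost, n = 54: SE = 1/√54 = 0.136; 0.04/0.136 = 0.29; coverage ≈ 0.94.
- 20% lost, n = 48: SE = 1/√48 = 0.144; 0.16/0.144 = 1.11; coverage ≈ 0.80.

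**Step 5: PGWB points.** At an assumed SD of 15, 0.04 × 15 = 0.6 and 0.16 × 15 = 2.4 points. For scale, the 95% half-width at n = 60 is 2.00/√60 = 0.26 SD, or 3.9 points.

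**Step 6: drop-out driven by the current, unseen score (MNAR).** The likelihood estimate is itself too favourable, by up to 0.09 SD at Week 52 with 20% loss and 0.13 SD with 30%. Observed cases reach 0.23 and 0.33 SD.

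**The case against.** A reader might infer that the Week 28 and Week 52 means will be inflated. The documents do not support that. Inflation requires an observed-case analysis, and the section that would say so is redacted. A t-test is compatible with observed cases, LOCF or multiple imputation, and under LOCF the MAR bias mostly runs the other way. Nor is the t-test itself the cause: with complete data both methods give the same mean. This objection stands, and the point is conditional for that reason.

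The textual hints are weak. In SAP 8.1, "descriptive statistics will include the number of subjects with non-missing data (n" is a general rule for summary tables, not a rule for gaps in the test. The final-visit row hints at observed cases, because under carry-forward to Week 64 it would largely repeat the Week 64 row. That is inference, not proof.

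The plan also limits the loss. Early-termination values can count at a visit, Protocol 10.2 asks for the visit form to be completed at premature withdrawal, and Protocol 7 asks for every attempt to keep visits. Step 3 shows that the mapping reduces the bias without removing it.

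The drop-out mechanism is assumed. Treatment failure is one of several listed withdrawal reasons and is the investigator's judgement, while PGWB is a self-report of general well-being. If loss follows skin disease or unseen change, a PGWB-only model need not remove the bias. That also stands and is why the fix includes an MNAR analysis.

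Finally, at 5-10% loss the observed-case bias is at most about 0.11 SD, less than half the interval's half-width. That limits the urgency. It is no reason to keep the t-test as primary, since the bias is systematic and the alternative needs no new data.

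**Conclusion.** The point holds as a recommended, inexpensive improvement, not as a demonstrated error. The legible plan analyses the primary PGWB change one visit at a time and leaves the earlier scores unused, in a single-arm study that allows withdrawal for poor response.

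The size rests entirely on assumed drop-out, SD, correlation and slope. Even the direction depends on the redacted rule: upward for observed cases, mostly downward for LOCF. The case for the model does not depend on which of these it is. Under MAR its bias was within 0.01 SD in every setting, better than observed cases, mapped observed cases or LOCF. It would be nearly redundant only if 8.10.1 already specifies MAR-valid imputation. It does not cure drop-out that depends on unobserved scores.

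**What to change.** - Confirm what SAP 8.10.1 specifies for gaps at Weeks 28 and 52.
- In SAP 8.9.1, make the primary PGWB estimate a mixed model for repeated measures on change from baseline at all post-baseline visits: visit as a categorical effect, baseline score centred at its mean, unstructured covariance, Kenward-Roger degrees of freedom. Report the adjusted mean change at Weeks 28 and 52 with 95% intervals.
- Name the fallback order in advance, for example heterogeneous Toeplitz, then AR(1) or compound symmetry. Eight visits give 8 × 9/2 = 36 covariance parameters for about 60 subjects, so non-convergence is a real possibility.
- Keep the t-test as a supportive summary.
- Add an MNAR sensitivity analysis, for example a delta adjustment of the missing scores over a stated range.

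The cost is SAP text and a standard SAS procedure, with no new data or visits. If drop-out proves negligible, the estimate will be essentially the same as the t-test mean. The change should be made before efficacy data are summarised, including at the Week 28 interim analysis.

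### Does the planned summary of percent change on the NRS, DLQI and Patient Happiness scales need replacing because low or zero baselines distort its mean?

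*SAP*

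**What the plan says.** SAP 8.9.1 gives the same entry for I-NRS, P-NRS, S-NRS and Patient Happiness with Psoriasis Control: "Change from Baseline to Weeks 4, 8, 12, 16, 28, 40, 52 and 64, with percent Change from Baseline summarized". For the DLQI, the change is "in DLQI total score, with percent Change from Baseline summarized". SAP 8.1 sets out what a summary of a continuous variable contains: "descriptive statistics will include the number of subjects with non-missing data (n), mean, standard deviation (SD), median, minimum, and maximum values". So a mean percent change will appear for five scales at eight visits, plus the final visit.

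Zero is a valid NRS score, because SAP 3.2.2 item 9 lists "Proportion of patients with itch score of 0, pain score of 0, and scaling score of 0, respectively" as an endpoint. Item 3 does the same for a DLQI of 0 or 1. The only visible severity threshold for entry (Protocol 4.1) is 3% body surface area; some criteria are blacked out.

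The SAP restricts low baselines once in these sections, for the 5-point DLQI reduction: "Subjects must have Baseline DLQI score of ≥ 5 to be included in this analysis".

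The percentage-change formula in SAP 5, the text directly under 8.10 and the range of the Happiness scale are blacked out. A rule for zero baselines may be among them.

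**The concern.** A percent change divides by the subject's own baseline, so subjects with small baselines carry great weight in the mean. On the NRS and the DLQI, improvement cannot go beyond -100%, while worsening from a baseline of 1 has no comparable limit: 1 to 3 is +200%. A few such subjects could make a good result look mediocre. On a scale where higher is better, low baselines would push the mean the other way and exaggerate benefit. A subject at zero on the NRS or DLQI can only stay or worsen, so leaving that subject out of the percent column removes a non-improver.

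Low baselines are plausible here. Entry rests visibly on affected area, not on symptoms or DLQI, and Protocol 6.2 lets subjects continue psoriasis treatments already in use. The baseline floor in the 5-point DLQI analysis could be read as a sign that the authors saw the problem in one place and missed it elsewhere. At stake are the percentages that a reader might lift from the tables and compare across scales.

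**Working it through.** The plan states no figure to reproduce: there is no formal sample size calculation, and the documents give no baseline distributions. What follows uses assumed scores for 60 subjects, a 0-10 range for NRS and Happiness, a 0-30 range for DLQI, and the usual formula, 100 × (visit - baseline) / baseline.

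**1. The distortion exists.** NRS: 57 subjects go from 6 to 2 and 3 go from 1 to 3.

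- Mean percent change: (57 × -66.67 + 3 × 200) / 60 = -53.3%.
- Median percent change: -66.7%.
- Mean change: (57 × -4 + 3 × 2) / 60 = -3.7. Mean baseline: (57 × 6 + 3 × 1) / 60 = 5.75. Percent change of the group mean: -3.7 / 5.75 = -64.3%.

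Three subjects move the mean by about 11 points against the group-mean figure. The median does not move.

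**2. Its direction is not fixed.** Keep the same baselines, but let the three go from 1 to 0.

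- Mean percent change: (57 × -66.67 + 3 × -100) / 60 = -68.3%.
- Group-mean figure: (57 × -4 + 3 × -1) / 60 = -3.85, and -3.85 / 5.75 = -67.0%.

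The mean now shows slightly more improvement. Understatement needs worsening or noise among low-baseline subjects.

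**3. Happiness, assuming higher is better.** 54 subjects go from 5 to 9 and 6 go from 1 to 9.

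- Mean percent change: (54 × 80 + 6 × 800) / 60 = +152%.
- Median: +80%.
- Group-mean figure: 4.4 / 4.6 = +95.7%.

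This is the largest effect, but it rests on a range and anchors that cannot be seen. In simulation the gap at a baseline mean of 6 runs from about 4 to 37 points as the assumed baseline SD goes from 1 to 3.

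**4. Zero baselines.** 54 subjects go from 6 to 2 and 6 go from 0 to 3. Percent change has n = 54 and equals -66.7%. Absolute change has n = 60: (54 × -4 + 6 × 3) / 60 = -3.3. The six worsening subjects are in the absolute change and its interval. If they are simply left out of the percent column, the difference in n (60 - 54 = 6) shows how many.

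**5. Typical size, and whether the alternative does better.** The simulation draws rounded normal baselines clipped to the scale and applies a 70% reduction plus noise. Zero baselines are dropped from the mean and median percent only. The last column is the standard error of the mean percent change at n=60. Repeat runs differ by a few tenths.

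| Setting | Mean percent | Group-mean figure | Median percent | Gap between first two | Standard error |
|---|---|---|---|---|---|
| NRS mean 3, SD 2.5, noise SD 2 | -51.5 | -56.0 | -66.7 | 4.5 | 8.7 |
| DLQI mean 6, SD 5, noise SD 4 | -46.2 | -55.7 | -70.0 | 9.5 | 11.3 |

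At NRS mean 7 (SD 2, noise SD 2) the gap is 0.9 against a standard error of 3.8. Every gap is below one standard error. In both rows the group-mean figure lies further from the 70% put into the model than the median, which is already planned. Clipping at zero accounts for part of that shortfall.

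**The case for a change.** The best case for acting is that the change is cheap and loses no stated endpoint: SAP 3.2.2 names percent improvement only for PASI. The plan does not say which statistic will lead, the mean is the one most often quoted, and a rule for zero baselines, even if one sits in the blacked-out text, would not help with baselines of 1 or 2. All of that is true, and the arithmetic holds.

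It does not carry the conclusion. Leading with absolute change and its interval is what SAP 8.9.1 already describes. Giving the median and making exclusions visible is largely met by SAP 8.1. The only new element would be to put the percent change of the group mean in place of the mean of the subjects' percent changes. That is a different descriptive quantity, weighted toward subjects with high baselines, and it has no per-subject SD, minimum or maximum. Confined to these five scales, it would also leave a mixture of metrics, since SAP 8.9.1 plans percent change for the six PGWB sub-domains too.

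The DLQI floor is no precedent either. A subject below 5 cannot fall by 5 points, so that restriction concerns whether the response is attainable, not whether a ratio is stable. Nor does any visible endpoint or analysis compare percentages across scales.

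**Conclusion.** No change to the plan is needed. A mean of individual percent changes can mislead when some baselines are low, by about 11 points in a case built to show it and by about 0.9 to 9.5 points in the noisiest NRS and DLQI settings simulated. It could be larger on the Happiness scale if higher is better and baselines are widely spread. These sizes depend on assumed baselines, ranges and noise, and the direction can reverse.

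Following the SAP as written leads to the same conclusions. The t-test and interval are described for change from baseline, percent change on these scales is a descriptive extra, the primary PGWB endpoint is unaffected, and the table already holds a robust figure and its n. Replacing the mean trades one imperfect summary for another without clear gain. Authors who cite a percent change for these scales can cite the planned median and say how many subjects had no value because of a zero baseline. That is ordinary reporting judgement and needs no amendment. Because the formula and the text under SAP 8.10 are blacked out, it cannot be said that the SAP lacks a rule for zero baselines.
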